3.2. Trial Endpoints

Primary endpoints

• Overall response rate (ORR) by PET-CT scan following 4-8 cycles of nivolumab

Secondary endpoints

- Progression-free survival (PFS) at 1 year
- Overall survival (OS) at 1 year
- Proportion of patients proceeding to SCT (ASCT or alloSCT)
- Safety & toxicity of nivolumab, particularly autoimmune toxicity
- OS and PFS stratified by partial metabolic response (PMR) versus complete metabolic response (CMR) on FDG-PET
- Transplant-related mortality and rate of serious complications of allogeneic transplant (grade 3-4 graft-vs-host disease, hyperacute graft-vs-host disease and steroid-responsive febrile syndrome)

Exploratory endpoints

- Correlate PET positive disease with histological evidence of disease on biopsy to establish biopsy negative PMR rate (subject to patient consent)
- Correlate disease response, as assessed by FDG-PET and histology, with serological markers, including serum TARC
- Evaluate the correlation between response to nivolumab and biological parameters e.g. PD-1 expression on Reed-Sternberg cells

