8.2. Treatment Summary

Patients for whom eligibility for treatment is confirmed (see section 7.2 for details) will receive 4-8 x 14-day cycles of nivolumab. Nivolumab 240mg will be administered on day 1 of each 14 day cycle. Dose banding is not permitted.

Trial treatment should begin within 4 weeks following the PET-CT scan to confirm eligibility for trial treatment (PET0).

	1	2	3	4	5	6	7	8	9	10	11	12	13	14
Nivolumab 240mg IV	Х													

Patients will have a PET-CT scan after 4 cycles (PET4). This should be performed on cycle 4, day 11-13 to allow time for central review before the cycle 5 day 1 visit would be due. Please note that patients must not proceed to cycle 5 prior to receipt of the PET4 central review report.

- If PET-negative (Deauville 1-3), they will stop nivolumab. Further management will be at the discretion of the treating clinician and the patient will be followed up as per the trial protocol (see section 9.6.2).
- If the scan shows disease progression, they will stop nivolumab and have further salvage at their treating clinician's discretion. They will enter into annual follow up for the trial.
- If the scan is positive (Deauville 4-5) but there is no evidence of disease progression, the patient will have a further 4 cycles of nivolumab. Following this, they will be followed up as per the trial protocol (see section 9.6.2).

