9.4. Assessments during Treatment

During treatment the patient should be seen every 2 weeks and the following assessments performed within 3 days prior to the start of each cycle:

- Clinical examination
- Full blood count with differential
- Biochemistry (ALT/AST, total bilirubin, alkaline phosphatase, urea, creatinine, calcium, magnesium, sodium, potassium, LDH, albumin, urate, glucose)
- Tests for autoimmune conditions (amylase, lipase, ACTH)
- Cycles 3, 5 & 7: pregnancy test (urine or serum; WOCBP only)
- Cycle 4 and cycle 7: Thyroid function tests (TSH & Free T4; Free T3 to be performed if TSH/Free T4 abnormal)
- Adverse event assessment

The following investigations must be carried out on the day of nivolumab administration:

Oxygen saturation measured by pulse oximetry at rest

Blood samples for translational research

Blood samples are to be taken and sent to the central laboratory at the Weatherall Institute
of Molecular Medicine, Oxford within 3 days prior to the start of cycles 2, 4, 6 and 8, and
at the 1 month post-treatment visit (see section 10.2 and Laboratory Manual for more
details)

Scanning required after cycle 4

- PET-CT scan to be carried out on cycle 4, day 11-13 as per trial requirements on an approved scanner, and images sent to the PET core lab for central review (PET4; see trial Imaging Manual for details).
- Contrast enhanced CT scan (ceCT). If feasible, this should be performed at the same imaging session as the PET-CT. If performed at the same session, the ceCT scan should be performed after the low dose PET-CT (see trial Imaging Manual for details).

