10.2. Peripheral blood samples

Research peripheral blood samples will also be collected as follows:

Timepoint	Sample required
Within 3 days prior to start of cycle 1	50ml peripheral blood in EDTA
	5ml peripheral blood in serum gel tube
Within 3 days prior to start of cycle 2	20ml peripheral blood in EDTA
	5ml peripheral blood in serum gel tube
Within 3 days prior to start of cycle 4	20ml peripheral blood in EDTA
	5ml peripheral blood in serum gel tube
Within 3 days prior to start of cycle 6	20ml peripheral blood in EDTA
	5ml peripheral blood in serum gel tube
Within 3 days prior to start of cycle 8	20ml peripheral blood in EDTA
	5ml peripheral blood in serum gel tube
1 month post treatment follow up visit	20ml peripheral blood in EDTA
	5ml peripheral blood in serum gel tube

Samples should be sent by first class mail to the central laboratory at the Weatherall Institute of Molecular Medicine, Oxford. No processing of the sample is required at site prior to sending. Samples taken on a Friday should be refrigerated over the weekend and sent on the next working day. Please refer to the Laboratory Manual for more details of how to send and log blood samples.

EDTA samples will be analysed at the Weatherall Institute of Molecular Medicine, Oxford. Immunophenotyping by multicolour flow panels and/or CyTOF (depending on cell recovery) will be performed on the blood to identify immune signatures prior to, during, and after nivolumab treatment. This may give important predictive and pharmcodynamic information. Panels for myeloid and T cell markers will be used. For patients with circulating activated T cells, these will be sorted and analysed functionally. Sequencing of TCR will also be performed. Any leftover material will be stored in a biobank for future use in ethically approved research, subject to patient consent.

Serum samples will be processed by the Weatherall Institute and frozen in the first instance. They will then be transferred to the MRC-University of Glasgow Centre for Virus Research where measurement of TARC (CCL17) levels will be performed. It is anticipated that samples will be transferred in one batch once all patients have completed trial treatment, and all TARC analysis will be performed retrospectively. Any leftover material following this analysis will be stored in a biobank for future use in ethically approved research, subject to patient consent.

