18.2.2. Analysis of secondary endpoints and secondary analyses

Survival endpoints:

Progression free survival (PFS)

PFS time will be measured from the date of the PET scan after first or second line salvage treatment (PET0) until the date of progression or death (whichever comes first). Patients who are alive and progression free will be censored at the date last seen.

Overall survival (OS)

OS time will be measured from the date of the PET scan after first or second line salvage treatment (PET0) until the date of death. Patients who are alive will be censored at the date last seen.

Analysis of PFS and OS will take place once we have 1 year follow-up for all patients. Kaplan Meier survival analyses will be used for both.

Subgroup analyses will be performed for responders and non-responders i.e. do patients with a PMR do worse than those with a CMR after nivolumab treatment. Kaplan Meier survival analysis and Cox regression may be used, although this will be dependent on the numbers of patients with a response and the numbers of events.

PFS and OS will also be analysed by further treatment i.e. did the patient go on to have an allograft or autograft, though we acknowledge that numbers will be very small so analyses will be descriptive.

CMR/PMR rates

Proportions of patients achieving CMR and PMR will also be presented.

Adverse events:

Analysis will focus on grade 3/4 adverse events. The worst grade seen per patient will be shown for each event type.

AESIs will be reported in more detail, with autoimmune events of any grade presented. All analysis will be descriptive.

Transplant related mortality and the rate of serious complications of allo SCT will presented, though again, it is likely only descriptive statistics will be used.

Other analyses:

The association between pre-nivolumab biological parameters and response to nivolumab will be investigated. As numbers will be very small mostly descriptive statistics will be used i.e. numbers and percentages will be presented for binary/categorical data and means and medians (with ranges) for continuous measurements.

We will also look at changes in TARC levels in responders and non-responders.

PET negative patients not treated with nivolumab

We will look at PFS, OS and subsequent treatments for patients who are PET negative following first or second line salvage treatment (i.e. at PET0).

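### The 1-month post-treatment research sample is not required to precede the next lymphoma treatment, so the last TARC value may not reflect nivolumab (minor, exploratory endpoint)

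*Protocol*

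**What the plan says.** Section 3.2 lists as an exploratory endpoint: "Correlate disease response, as assessed by FDG-PET and histology, with serological markers, including serum TARC". Section 18.2.2 turns this into one sentence of analysis: "We will also look at changes in TARC levels in responders and non-responders". It names no time point. For the neighbouring analyses of biological parameters it warns: "As numbers will be very small mostly descriptive statistics will be used".

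Serum comes from the research blood schedule in section 10.2, where "measurement of TARC (CCL17) levels will be performed" on stored samples, probably in one batch after all patients have finished treatment. After a baseline sample before cycle 1, section 9.4 asks for samples "within 3 days prior to the start of cycles 2, 4, 6 and 8". The final sample is listed in section 10.2 as "1 month post treatment follow up visit", and section 9.6.2 sets it at 30 days after the last dose, ±3 days. The EDTA blood from the same visits is used for immunophenotyping before, during and after nivolumab.

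The PET4 result decides how long treatment lasts (sections 3 and 8.2, Appendix 3). Patients in CMR and patients with progression stop after four cycles. Those with PMR, no metabolic response or an indeterminate response may go on to eight. On progression at PET4, section 8.2 says: "If the scan shows disease progression, they will stop nivolumab and have further salvage at their treating clinician's discretion". For patients in CMR, section 2.1 makes transplant the priority.

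**The concern.** The final research sample is tied to one date only, that of the last nivolumab dose. Neither section 9.6.2 nor section 10.2 says what happens if another lymphoma treatment begins first. The patients who stop at PET4 are those with a reason to move on soon: progressors need disease control, and patients in CMR are being taken towards transplant. A sample drawn after salvage or pre-transplant therapy has begun measures TARC and immune phenotype under that therapy. If it is then used to describe change on nivolumab, the two treatments cannot be separated.

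Section 2.1 gives TARC a purpose: PET may be falsely positive under PD-1 blockade, and TARC is named as an alternative measure of response. With 30 treated patients (section 18.1), a few affected or absent samples could change a descriptive picture.

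A second problem concerns the same draw: the protocol gives two answers on whether a progressor attends the 1-month visit.

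**Working it through.** The plan gives no figure of its own on this point, so the check is a timeline built from its schedule.

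**Inputs.** 14-day cycles (8.2); PET4 on cycle 4 day 11-13 (8.2, 9.4) and PET8 on cycle 8 day 11-13 (9.5); on-treatment samples within 3 days before the cycle (9.4, 10.2); last sample 30 ±3 days after the last dose (9.6.2). Assumption: no dose delays.

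**Formula.** Let day 0 be cycle 1 day 1. Cycle k starts on day 14(k − 1), and day d of cycle k is day 14(k − 1) + d − 1.

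**Patient who stops after four cycles**
- Last dose: 14 × 3 = day 42.
- PET4: 42 + 10 to 42 + 12 = days 52-54.
- Last sample: 42 + 27 to 42 + 33 = days 69-75.
- PET4 to last sample: shortest 69 − 54 = 15 days, longest 75 − 52 = 23 days.
- Cycle 5 would have started on day 56, so 69 − 56 = 13 to 75 − 56 = 19 days remain after the first dose not given.

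**Patient who completes eight cycles**
- Last dose: 14 × 7 = day 98; PET8: days 108-110; last sample: days 125-131.
- PET8 to last sample: again 125 − 110 = 15 to 131 − 108 = 23 days.

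On either path there are two to three weeks between the scan that ends treatment and the last sample. The protocol sets no waiting period for the next treatment in that interval and no rule on the order of the two.

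**Samples that cannot be affected.** The samples before cycles 1, 2 and 4 fall on days −3 to 0, 11-14 and 39-42. All precede PET4, and every patient who reaches cycle 4 has them due. The samples before cycles 6 and 8 (days 67-70 and 95-98) are due only in patients who continued after PET4, and they are taken while the patient is still on nivolumab. The exposure to later therapy is therefore confined to the 1-month sample.

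**Does a progressor give the 1-month sample?**
- Section 8.2: progression at PET4 leads to annual follow-up. Section 9.8: after progression, patients are seen annually. On this reading there is no 1-month visit and no sample.
- Section 8.4: progressive disease is among the reasons for permanent discontinuation, after which follow-up is under section 9.6.2. Section 9.6.2 covers patients who received nivolumab and includes the 1-month visit with the research blood. On this reading the sample is due.

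Both cannot apply to the same patient. On the first reading the last sample is missing because of response; on the second it is drawn but may follow salvage.

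**Precedent in the protocol.** Section 12.2.1 already ends adverse event recording at the earlier of a fixed time or the start of the next lymphoma treatment. The research sample has no such bound.

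**The case against.** The strongest reply is that the protocol states no faulty analysis. The TARC endpoint is exploratory, numbers are small, and section 18.2.2 commits to no time point. Choosing one, and deciding how to treat samples taken after new therapy, is usual content for a statistical analysis plan. A like-for-like contrast is available from samples already scheduled: the change from before cycle 1 to before cycle 4. Assays are run retrospectively and section 11.3 collects a new treatment form, so affected samples could be flagged before any result exists. All of this stands, and it is why the absence of a time point is not part of the point.

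A reader might go further and infer that responders and non-responders are not measured over comparable time, because patients in CMR or with progression at PET4 have no cycle 6 or 8 sample, and that this pulls the two groups together. The documents do not support that. Responders mix four-cycle patients (CMR at PET4) with eight-cycle patients (PMR or later response). Non-responders mix four-cycle progressors with eight-cycle patients without response. Any imbalance depends on how patients divide at PET4, which the protocol does not give. A direction is no better founded, since CMR patients as well as progressors may start new therapy before the sample.

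It is also fair to say that treatment starting before day 30 is inferred. Section 12.2.1 expects most patients to have moved on by 3 months, which says nothing definite about the first month. And if sections 8.2 and 9.8 govern, progressors have no 1-month sample to contaminate.

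What the reply does not answer is the sampling rule itself. It belongs to the protocol. An analysis plan can discard a sample drawn after new therapy, but it cannot recover the value that an earlier draw would have given.

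**Conclusion.** The point holds as a minor one, for an exploratory endpoint only. The 1-month sample may be drawn after the next lymphoma treatment has begun, within a 15 to 23 day interval after the deciding scan, so the last TARC and immunophenotyping values may reflect that treatment. Contamination is possible, not certain; its frequency, size and direction cannot be derived from the protocol. The interval rests on nominal 14-day cycles and the stated windows; a delayed scan or sample would shift it.

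The conflict over follow-up of progressors is plain on the text and does not depend on any assumption about when new treatment starts. The primary endpoint, the secondary endpoints, the safety reporting and the sample size of 30 are unaffected.

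**What to change.** In sections 9.6.2 and 10.2, take the existing post-treatment research sample at 30 days after the last dose (with the present window) or before the first dose of the next lymphoma treatment, whichever is earlier, and record the actual date of the draw. Leave any sample taken after new treatment began out of the nivolumab TARC comparison. Reconcile sections 8.2 and 9.8 with sections 8.4 and 9.6.2, so that it is clear whether patients with progression at PET4 give this sample.

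The cost is one clause on an existing draw, a recorded date and the reconciled wording. No extra blood is taken and no treatment decision changes. The downside is that some samples will be drawn before day 30, so time since the last dose will vary between patients and will depend partly on their clinical course. The recorded date allows this to be shown.

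One suggestion for the analysis plan, not a protocol defect: use the change from before cycle 1 to before cycle 4, among patients who reach cycle 4, as the like-for-like contrast, and report cycle 6 and 8 values only for those who continued. Patients who stop during cycles 1-3 may have no pre-cycle 4 sample, yet count as non-responders in the primary analysis if they have no response scan (section 18.2.1), so their number should be stated.

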19. ETHICAL AND REGULATORY CONSIDERATIONS

In conducting the trial, the Sponsor, UCL CTC and sites shall comply with all relevant guidance, laws and statutes, as amended from time to time, applicable to the performance of clinical trials including, but not limited to:

- the principles of ICH Harmonised Tripartite Guideline for Good Clinical Practice as set out in Schedule 1 (Conditions and Principles of Good Clinical Practice and for the Protection of Clinical Trial Subjects) of the Medicines for Human Use (Clinical Trials) Regulations 2004 and the GCP Directive 2005/28/EC, as set out in SI 2006/1928
- Human Rights Act 1998
- Data Protection Act 19982018
- Freedom of Information Act 2000
- Human Tissue Act 2004
- Medicines Act 1968
- Medicines for Human Use (Clinical Trials) UK Regulations SI 2004/1031, and subsequent amendments
- Good Manufacturing Practice
- the UK Policy Framework for Health and Social Care Research, issued by the Health Research Authority

Where applicable, UCL CTC and sites will work towards implementation of the EU Clinical trials Regulation EU/536/2014.

19.1. Ethical Approval

The trial will be conducted in accordance with the World Medical Association Declaration of Helsinki entitled 'Ethical Principles for Medical Research Involving Human Subjects' (1996 version) and in accordance with the terms and conditions of the ethical approval given to the trial.

The trial has received a favourable opinion from the London – South East Research Ethics Committee (REC) and Health Research Authority (HRA) approval for conduct in the UK.

UCL CTC will submit Annual Progress Reports to the REC, commencing one year from the date of ethical approval for the trial.

19.2. Regulatory Approval

A Clinical Trial Authorisation (CTA) has been granted for the trial.

The trial will be conducted at approved trial sites in accordance with the trial protocol and the terms of the CTA granted by the MHRA.

19.3. Site Approvals

Evidence of assessment of capability and capacity by the Trust/Health Board R&D for a trial site must be provided to UCL CTC. Sites will only be activated when all necessary local approvals for the trial have been obtained.

19.4. Protocol Amendments

UCL CTC will be responsible for gaining ethical and regulatory approval, as appropriate, for amendments made to the protocol and other trial-related documents. Once approved, UCL CTC will ensure that all amended documents are distributed to sites as appropriate.

Site staff will be responsible for acknowledging receipt of documents and for implementing all amendments promptly.

19.5. Patient Confidentiality & Data Protection

Patient identifiable data, including initials, date of birth and NHS number (or equivalent) will be required for the registration process and will be provided to UCL CTC. UCL CTC will preserve patient confidentiality and will not disclose or reproduce any information by which patients could be identified. Data will be stored in a secure manner and UCL CTC trials are registered in accordance with the Data Protection Act 1998-2018 with the Data Protection Officer at UCL.

20.2. Indemnity

University College London holds insurance against claims from participants for injury caused by their participation in the clinical trial. Participants may be able to claim compensation if they can prove that UCL has been negligent. However, as this clinical trial is being carried out in a hospital, the hospital continues to have a duty of care to the participant of the clinical trial. University College London does not accept liability for any breach in the hospital's duty of care, or any negligence on the part of hospital employees. This applies whether the hospital is an NHS Trust or otherwise.

Participants may also be able to claim compensation for injury caused by participation in this clinical trial without the need to prove negligence on the part of University College London or another party. Participants who sustain injury and wish to make a claim for compensation should be advised to do so in writing in the first instance to the Chief Investigator, who will pass the claim to the Sponsor's Insurers, via the Sponsor's office.

Hospitals selected to participate in this clinical trial shall provide clinical negligence insurance cover for harm caused by their employees and a copy of the relevant insurance policy or summary shall be provided to University College London, upon request.

21. FUNDING

Bristol-Myers Squibb are supporting the central coordination of the trial through UCL CTC, translational research at HMDS and the Weatherall Institute of Molecular Medicine, Oxford, and supplying Nivolumab free of charge for use in the trial.

Research costs will be reimbursed to sites as per the finance section of the CTSA.

22. PUBLICATION POLICY

The results of the ANIMATE trial will be presented at relevant conferences and published in a peer reviewed journal. The primary publication from the ANIMATE trial will be written by the TMG. Authors will include the CI, TMG members, representatives of UCL CTC including the trial coordinator and trial statistician, and PIs at sites that make a significant contribution to patient recruitment.

Abstracts and papers will be reviewed by BMS prior to submission in accordance with the requirements of the Trial Drug Supply Agreement.

The Clinicaltrials.gov number of the trial and the funder reference number will be quoted in all publications.

Central laboratories and the PET core laboratory may not publish any data pertaining to ANIMATE patients without prior written permission from the TMG.

Sites may not publish any data pertaining to ANIMATE patients without prior written permission from the TMG.

Data generated from the ANIMATE trial will be the property of UCL as Trial Sponsor.

